Study Title: Does the use of continuous glucose monitoring (CGM) in the immediate postpartum period in women with pregestational diabetes admitted to the hospital decrease hypoglycemic episodes?

NCT number: 06141941

Date: January 1, 2023

PI: [name]

Research hypothesis:

The use of continuous glucose monitoring (CGM) to monitor glucoses in patients hospitalized in the immediate postpartum period is more effective at identifying patients with hypoglycemia than the traditional point of care (POC) blood glucose testing.

Population: pregnant women with type 1 or type 2 diabetes

Inclusion criteria: Pregnant women with type 1 or type 2 diabetes managed with insulin, who own a smart device (which will serve as a receiver for the CGM device).

Exclusion: patients less than 18 years of age, non-English speaking patients, gestational diabetes, extensive skin changes/diseases that inhibit wearing a sensor on normal skin, known allergy to adhesives

Number of subjects proposed to complete this study:

This is a pilot study to evaluate the role of a CGM device to decrease hypoglycemic events in hospitalized patients in the postpartum period, a power analysis has not been pre-specified.

30 patients were chosen as this appears to be attainable number based on the number of DM1/DM2 pregnant patients which are seen in the high-risk OB clinic.

Patient recruitment:

Pregnant patients with type 1 or type 2 diabetes managed with insulin will be approached during their OB clinic visit during the third trimester prior to 28 weeks, to describe the study and assess if they would be interested in participating. If they meet inclusion criteria and opt to enroll in the study, they will be consented during that visit. If patients would like time to discuss study with family/friends, they will be given up until the time of delivery (~10-12 weeks) to determine if they would like to participate in the study. During the consenting process, patients will be aware that participation in this study will not have any effect on routine standard of care.

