If patients opt to enroll in the study, a CGM device will be placed by research personnel during their clinic visit if seen within 3 days of their planned induction of labor or planned cesarean section. If a patient is not seen for a prenatal visit 3 days prior to their delivery (i.e. missed clinic appointment), the device will be placed upon arrival to L&D for delivery. Patient will be assisted in getting the Dexcom G6 app on their cell phone to be the receiver of glucose data.

Patients who are currently using the Dexcom CGM for routine monitoring of their glucoses, will be allowed to continue using their own sensor and transmitter. Upon presentation to Labor and Delivery, patients will be assisted in activating the Share App on their cell phone.

Labor and Delivery Nursing Staff will be given a Samsung phone with the Follow app in order to receive glucose data. The Samsung phone will be transferred to the Mother/Baby Unit with the patient after delivery.

CGM sensors and transmitters will be kept locked in the MFM offices in a secure file cabinet. Study personnel will have a key to the file cabinet and access to the devices. Upon arrival of a study

patient to labor and delivery, study personnel will remove a sensor and transmitter from the secure file cabinet in order to place the CGM on the patient.

Glucose values from the CGM device will then be available to nursing through the Samsung phone. Nursing will be able to see current glucose data on their patient and would receive alarms to indicate hypoglycemia or impending hypoglycemia. Nursing will be provided with instructions for how to access the CGM follow app and how to appropriately respond to the alarms. Nursing will continue to perform standard POC blood glucose monitoring per routine protocol but will also obtain a finger stick to validate a blood glucose level whenever a low CGM alarm sounds. Low blood glucose values <70 mg/dl will be treated per hospital nursing policy. Monitoring of glucose levels through the CGM device will continue throughout the postpartum hospital stay. Patients who do not use CGM as part of their routine care, will have their CGM sensor and transmitter removed prior to discharge from the hospital.

Following discharge from the hospital, there will be no additional long-term follow-up.

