Participants will be provided compensation of \$25 e-voucher upon completion of the study and discharge from the hospital. The e-voucher is provided through University Accounting Services.

Data collection and analysis:

Data variables to be collected include the type of diabetes (DM1/DM2), POC glucose values, number of hypoglycemic events, number of times treated for hypoglycemia.

Subjects will be de-identified with the use of a separate document correlating subjects medical record number with the study ID number. The study data will be entered into a REDCap database. At the conclusion of the research project, the key will be destroyed.

With DEXCOM CGM services, glucose values will be uploaded to a DEXCOM password protected website to see glucose values in real time.

Continuous variables will be analyzed using a fishers exact t-test (i.e. blood sugar measurements). Categorical variables will be compared using a chi square analysis (i.e. hypoglycemic events). $P < .05$ will be considered statistically significant.

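### The test named for blood sugar does not exist, and the plan does not define the comparison, the unit of analysis or the handling of repeated readings

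*Combined protocol and SAP*

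**What the plan says.** The combined protocol and SAP covers its statistics in three sentences at the end of Data collection and analysis. For glucose: "Continuous variables will be analyzed using a fishers exact t-test (i.e. blood sugar measurements". For events: "Categorical variables will be compared using a chi square analysis (i.e. hypoglycemic events". The third sets the threshold, a P-value below .05, which "will be considered statistically significant". Nothing else in the document describes how glucose values will be analysed. No groups or methods to be compared, unit of analysis, pairing or confidence intervals are named.

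The data structure has to be read from other sections:

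- The Research hypothesis is that CGM "is more effective at identifying patients with hypoglycemia than the traditional point of care (POC) blood glucose testing".
- The procedures under Patient recruitment apply both methods to every participant, and the extra finger stick follows each low alarm from the CGM: "Nursing will continue to perform standard POC blood glucose monitoring per routine protocol but will also obtain a finger stick to validate a blood glucose".
- Readings accumulate over days: "Monitoring of glucose levels through the CGM device will continue throughout the postpartum hospital stay".
- The data-collection list names diabetes type, POC values, and counts of low-glucose events and of treatments for them. CGM values are not on it. They are described only as going to the manufacturer's website for real-time viewing.
- On size, "30 patients were chosen as this appears to be attainable number", and "a power analysis has not been pre-specified".

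**The concern.** The only method named for glucose joins two procedures with different purposes. Fisher's exact test is for contingency tables of counts and does not apply to a continuous measurement. A t-test applies to means, but the plan does not say means of what, between which groups, or with what treated as an independent observation.

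The last omission matters most. Readings from one patient resemble each other, and CGM and POC values taken close together share the same underlying glucose. An analyst who drops the words Fisher's exact and runs a t-test on all readings gets a wrong standard error. It is too small if pairs are pooled as though from different people, and too large if the pairing is ignored. The P-value set against .05 would then depend on a choice the plan leaves open.

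There is also a question of relevance. A difference in mean glucose does not show which method better identifies patients with lows. CGM samples continuously and POC at chosen times, so the two means can differ despite good agreement, or match despite poor agreement at low values.

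**Working it through.** **From the documents.** 30 patients and a 0.05 threshold (two-sided assumed). No SD, effect size, power or number of readings is given, so there is no planned figure to reproduce.

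**Assumed, not in the documents.** m = 4 to 20 readings per patient; intraclass correlation (ICC) 0.1 to 0.5, the same value used for glucose level and for CGM-minus-POC differences; glucose SD 40 mg/dL; difference SD 15 mg/dL; a 15/15 split of DM1 and DM2.

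**Step 1: pooled paired t-test, closed form.** The design effect is DE = 1 + (m − 1) × ICC. The actual type I error is 2 × [1 − Φ(1.96/√DE)].

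- m = 4, ICC 0.1: DE = 1 + 3 × 0.1 = 1.3, type I 8.6%.
- m = 20, ICC 0.5: DE = 1 + 19 × 0.5 = 10.5, type I 54.5%.
- ICC 0 (no patient-level component in the differences): DE = 1, type I 5%.

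**Step 2: pooled unpaired t-test, closed form.** Per reading, the test uses a variance of 40² + (40² + 15²) = 3425. The true variance of the mean difference corresponds to 15² × DE = 225 × DE.

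- m = 20, ICC 0.5: √[3425/(225 × 10.5)] = 1.20, so the standard error is about 20% too large and type I falls to about 2%.
- m = 4, ICC 0.1: √[3425/(225 × 1.3)] = 3.42, and type I is essentially zero.

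**Step 3: simulation under the null, 4,000 runs per setting.** Selected settings, type I error:

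| m | ICC | Pooled paired | Pooled unpaired | Patient means, paired | DM1 v DM2, pooled POC | DM1 v DM2, patient means |
|---|---|---|---|---|---|---|
| 4 | 0.1 | 0.080 | 0.000 | 0.050 | 0.085 | 0.049 |
| 8 | 0.3 | 0.261 | 0.000 | 0.046 | 0.260 | 0.048 |
| 12 | 0.3 | 0.349 | 0.000 | 0.053 | 0.352 | 0.049 |
| 20 | 0.5 | 0.534 | 0.025 | 0.053 | 0.565 | 0.050 |

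Over all twelve settings, patient-level tests lie between 0.046 and 0.055. Simulation error is about ±1.96 × √(0.05 × 0.95/4000) = ±0.007, so this is the nominal 5%.

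**Step 4: a second set of assumptions.** 30 patients × 15 pairs; between-patient SD 25, within-patient SD 35, device error SD 15, patient-specific device bias SD 8 mg/dL. Standard errors of the mean difference:

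- True: √[(8² + 15²/15)/30] = √(79/30) = 1.62 mg/dL.
- Pooled paired: √[(64 + 225)/450] = √(289/450) = 0.80. Type I is 2 × [1 − Φ(1.96 × 0.80/1.62)], about 33%.
- Pooled unpaired: POC variance 25² + 35² = 1850 and CGM variance 1850 + 289 = 2139, giving √(3989/450) = 2.98. Type I is below 0.1%.

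The directions of error are the same as before.

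**Step 5: alarm-triggered finger sticks.** These are taken because CGM reads low. With Step 4's SDs, the slope of the CGM-minus-POC difference on the CGM value is 289/2139 = 0.135. Assume an alarm at 70 mg/dL and mean glucose 120 (range 100 to 140). With zero true bias, the expected difference at the alarm is 0.135 × (70 − 120) = −6.8 mg/dL (−4.1 to −9.5). Pooling such pairs with routine ones would therefore suggest a device bias that is not there.

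**The case against.** A reader might infer that the plan commits to an independent-observations analysis of paired CGM and POC readings, and so to invalid standard errors. The documents do not support that. No paired glucose analysis is written down, and CGM values are not on the collection list. The comparison could be DM1 against DM2 on POC values alone. A test that cannot be run yields no standard error, and with no unit of analysis stated, a t-test on patient means remains an open reading that holds about 5%. This stands, and it makes the error in inference conditional on pooling.

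The sizes also rest on assumed SDs, correlations and reading counts. In particular, the inflation in the naive paired test comes from an assumed patient-level component in device differences. Without one, that test would be close to valid. This stands too: the percentages are illustrations, not properties of this trial.

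Finally, this is a pilot without a power analysis, and its hypothesis concerns hypoglycemia, which the plan assigns to the chi-square sentence. That limits the reach of the defect to the glucose comparison. It does not excuse naming a non-existent test and judging it at .05. If only POC values are compared between diabetes types, pooling still inflates the type I error, from 8.5% to 56.5% in the settings tried.

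**Conclusion.** The concern holds in a limited form. The glucose analysis cannot be executed as written, and nothing elsewhere in the document shows what was meant. Correcting it to a plain t-test would leave the comparison, the unit of analysis and the repeated readings undefined. If readings were pooled as independent, type I error would be about 8–53% for a paired CGM-POC test and 0–2.5% for an unpaired one, against about 5% with the patient as unit. These ranges assume 30 patients, 4 to 20 readings each and ICC 0.1 to 0.5. The sentence should be replaced before any data are analysed.

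**What to change.** Replace the blood sugar sentence with one that names the comparison and the data source.

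- **If CGM is compared with POC:** match each POC value to a CGM value by time, with the window stated in advance. Analyse CGM-minus-POC differences with a linear mixed model with a patient random intercept, or a paired test on patient-level means. Report mean bias and repeated-measures limits of agreement with 95% confidence intervals.
- **If POC values are compared between DM1 and DM2:** use patient means or the same random intercept.
- **In the CGM-POC analysis:** report routine POC pairs separately from alarm-triggered finger sticks, because the latter are selected on a low CGM value and a random intercept does not remove that selection.
- **Scope:** state that this agreement analysis supports, but does not itself test, the hypothesis about identifying patients with hypoglycemia.

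The cost is small but goes beyond wording. CGM values and time stamps for both methods must be added to the data-collection list and linked to the study ID before the key is destroyed at the end of the project. The analysis itself is slightly more work than a t-test. No extra patients or additional glucose measurements are needed.

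### The chi-square planned for hypoglycemic events has no stated groups or unit, and for the hypothesised CGM-versus-POC comparison it ignores that every patient has both methods and can have repeated events

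*Combined protocol and SAP*

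**What the plan says.** The Research hypothesis is that CGM "is more effective at identifying patients with hypoglycemia than the traditional point of care (POC) blood glucose testing". It is the only hypothesis, it compares two methods, and its unit is the patient.

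The section on the number of subjects describes one pilot cohort: "30 patients were chosen as this appears to be attainable number", and "a power analysis has not been pre-specified". No control group or randomisation appears.

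The procedures set out under Patient recruitment apply both methods to every participant. Each wears a CGM, and "Nursing will continue to perform standard POC blood glucose monitoring per routine protocol". A low alarm from the device prompts an extra, confirmatory finger stick. On duration, "Monitoring of glucose levels through the CGM device will continue throughout the postpartum hospital stay".

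The analysis text says "Categorical variables will be compared using a chi square analysis (i.e. hypoglycemic events", with significance at P below 0.05. The collected variables are diabetes type, POC glucose values, the number of hypoglycemic events and the number of times treated. CGM readings are not on that list. No paired test and no method for repeated events is named.

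**The concern.** If the chi-square is the test of the hypothesis, it sets CGM detections beside POC detections as though they came from separate patients. In paired data the evidence on which method finds more patients lies in the discordant patients, those found by one method only. An ordinary chi-square looks only at the two margins and discards that information.

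There is also a mismatch of unit. The hypothesis concerns patients, but the recorded outcome is a number of events, and one patient can contribute several. Those events are not independent categorical observations.

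At stake is the one formal test the plan attaches to hypoglycemia. With 30 patients chosen for feasibility, it could miss a real gain in detection. If events are pooled, it could report a difference that is not there.

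**Working it through.** **Inputs.** From the documents: n = 30 in one cohort, and a 0.05 threshold (two-sided assumed, as sidedness is not stated). The documents give no rate, effect size or correlation, so the plan has no figure to reproduce, and every rate below is an assumption used for illustration.

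**1. One possible result.** Of 30 patients, 8 are found by both methods, 6 by CGM only, 0 by POC only and 16 by neither.

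- Chi-square on 8/30 against 14/30: pooled p = 22/60 = 0.3667. X² = (14/30 − 8/30)² / [0.3667 × 0.6333 × 2/30] = 0.0400 / 0.01548 = 2.58, so P = 0.108. With continuity correction the numerator is (5/30)² = 0.0278, X² = 1.79 and P = 0.180.
- Exact McNemar on the 6 discordant patients, all one way: P = 2 × 0.5⁶ = 0.031.

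The same data fall on opposite sides of 0.05.

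**2. Power.** Assume 50% of patients have a low, CGM catches 90% of them, and the two detections are independent given a low.

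- POC catches 50%: CGM only = 0.5 × 0.9 × 0.5 = 0.225; POC only = 0.5 × 0.5 × 0.1 = 0.025.
- POC catches 60%: CGM only = 0.5 × 0.9 × 0.4 = 0.18; POC only = 0.5 × 0.6 × 0.1 = 0.03.

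Summing over all possible paired 2×2 tables with n = 30:

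| POC catches | Chi-square | Exact McNemar | Asymptotic McNemar |
|---|---|---|---|
| 50% | 30% | 48% | 65% |
| 60% | 12% | 26% | 45% |

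**3. Type I error at patient level.** Keep 50% with a low and give both methods the same catch rate, from 50% to 90%. Chi-square then rejects in 1.7% of trials at a 50% catch rate, 0.4% at 70%, and under 0.1% at 90%. Exact McNemar is also conservative, at 0.1% to 1.8%. Asymptotic McNemar gives 2.6% to 4.8%.

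**4. Dependence on correlation.** Fix the detection rates at 30% (POC) and 50% (CGM) and vary the within-patient correlation. Power is:

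| Correlation | Chi-square | Exact McNemar | Mid-P McNemar | Asymptotic McNemar |
|---|---|---|---|---|
| 0 | 35% | 26% | 33% | 34% |
| 0.3 | 32% | 34% | 43% | 43% |
| 0.5 | 29% | 44% | 57% | 59% |
| 0.6 | 27% | 52% | 67% | 75% |

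At zero correlation pairing gains nothing, and the exact test does worse than chi-square. The gain grows with the correlation.

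**5. Pooled readings.** This was simulated with 30 patients, about 10% low readings, 8 to 20 readings per patient and method, and no true difference between methods. If patient risk is fully shared by the two methods, chi-square rejects about 3% to 5% of the time. If patient effects are partly method-specific, it rejects about 7% to 20%. The documents do not say which case applies, so neither direction nor size can be fixed from them.

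**The case against.** The strongest reply is that the plan never says the chi-square compares CGM with POC. It names no groups, CGM readings are not among the collected variables, and the study title asks about a decrease in episodes, which is a different question with no comparator. This stands in part. A reader might infer that the plan explicitly treats the two methods as independent groups. The documents do not say so; the contrast is inferred from the hypothesis and the single cohort. It is still the only comparison the hypothesis makes, and no other test of it is offered.

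A second reply is that the loss of power is conditional. That also stands. It requires positive correlation, which is likely because both methods observe the same patient and a low alarm prompts a finger stick, but its size is not given. The exact McNemar test is itself conservative at this sample size.

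A reader might also infer a badly inflated error rate for a comparison of type 1 with type 2 diabetes on pooled events. Clustering could cause that, but diabetes type is only a listed variable. The plan states no such comparison, so no weight is placed on it here.

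Finally, this is a declared pilot. That excuses the lack of a power calculation. It does not excuse a significance rule tied to a test that does not fit the design.

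**Conclusion.** The rule is wrong as written for the study's own hypothesis. It rests on independence where the design gives paired detections and repeated events, and this is more than a missing detail. That conclusion needs only the documents, together with the inference that the test is meant for CGM against POC.

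The size rests on assumptions. At patient level with positive correlation, chi-square is conservative, and in the assumed scenarios it gives up about 18 points of power (30% to 48%) or 14 points (12% to 26%) against exact McNemar, and 33 to 35 points against asymptotic McNemar. It would be too strong to say that power is always lost, or that the true error rate is one particular figure: with no correlation there is no loss, and the patient-level rejection rate under no difference moves with the assumed catch rate. For pooled events the error may run the other way, toward a falsely small P value, and its size cannot be derived from the documents.

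**What to change.** In Data collection and analysis:

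1. State the primary comparison: patient identified with hypoglycemia (yes/no) by CGM against the same patient identified by routine POC testing, with the rule for a positive result by each method written down.
2. Analyse it with a McNemar test, asymptotic or mid-P because the exact version is conservative at n = 30. Report the paired difference in proportions with its 95% CI.
3. Analyse event counts with a patient-clustered count model, such as Poisson or negative binomial GEE with patient-days as offset, in place of chi-square.
4. Add CGM readings to the collected variables, and flag each POC stick in the dataset as routine or alarm-triggered. Count POC detection from routine sticks only. Otherwise the paired test would compare CGM with POC results that CGM itself prompted.

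The cost is a few lines of analysis text, the extraction of CGM readings that are already uploaded to the device website, and one extra data field. Sample size and patient procedures do not change.

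### An unpowered pilot of 30 offers only P<.05 on unranked variables, with no primary outcome and no interval estimate

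*Combined protocol and SAP*

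**What the plan says.** Under *Number of subjects proposed to complete this study*, the protocol states: "This is a pilot study to evaluate the role of a CGM device to decrease hypoglycemic events". It adds that "a power analysis has not been pre-specified" and gives the basis for the number: "30 patients were chosen as this appears to be attainable number".

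Under *Data collection and analysis*, the variables to be collected are diabetes type and "POC glucose values, number of hypoglycemic events, number of times treated for hypoglycemia". None is called primary, secondary or exploratory. The analysis text is three sentences. The first reads "Continuous variables will be analyzed using a fishers exact t-test (i.e. blood sugar measurements", with the bracket then closed. The second assigns a chi-square analysis to categorical variables, with hypoglycemic events as the example. The third says that P<.05 "will be considered statistically significant". There is no effect estimate, confidence interval, multiplicity rule or statement that the tests are exploratory.

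The title asks whether CGM decreases hypoglycemic episodes. The research hypothesis is that CGM is better than POC testing at identifying patients with hypoglycemia. Under *Patient recruitment*, the same patients have both methods: routine POC testing continues, and a finger stick is added whenever a low CGM alarm sounds.

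**The concern.** A pilot may go without a power calculation, and this one says so openly. The difficulty is that, having set that basis aside, the plan gives its reader only a significance threshold by which to judge the results. Two things follow.

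First, a P value above .05 from 30 patients may reflect no gain or a useful gain that the study was too small to show. Without an interval, the report cannot separate the two.

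Second, no variable is ranked, and the title and hypothesis do not settle which one matters most. They can even pull in opposite directions, because better detection can raise the number of recorded events while the title looks for a fall. An analyst who finds one P<.05 has no prior statement of whether it is the main result.

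What is at stake is the use of the pilot. A later trial needs an estimate of the extra detection and its uncertainty, and the plan does not promise either.

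**Working it through.** **No figure to reproduce.** The 30 rests on attainability. The documents give no effect size, event rate, SD or power, so every detection rate below is an assumption. Sidedness is not stated; two-sided .05 is assumed.

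**1. Chance findings.** For k independent tests at .05 with no true differences, P(at least one below .05) = 1 − 0.95^k.
- k = 2 (the two kinds of variable that the test sentences use as examples): 1 − 0.9025 = 0.0975, or 9.8%.
- k = 3 (if times treated is tested as well): 1 − 0.857375 = 0.1426, or 14.3%.
- Simulating three correlated normal statistics gives about 12.5% at r = 0.5 and 9.8% at r = 0.8.

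Correlation is likely, since the nursing policy treats low values and so ties treatments to events.

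**2. What a null result would mean (illustration only).** Both methods are used in the same patients, so a paired comparison of detection is a natural reading. The plan does not specify one. Take an exact McNemar test in which discordance runs one way: some patients are found by CGM only and none by POC only.
- Five such patients: p = 2 × 0.5^5 = 0.0625. Six: p = 2 × 0.5^6 = 0.03125. At least six are needed.
- The chance of P<.05 is then P(Bin(30, π) ≥ 6), where π is the true CGM-only detection rate:

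| Assumed π | Chance of P<.05 |
|---|---|
| 10% | 7% |
| 20% | 57% |
| 30% | 92% |

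- If 5% of patients are instead found only by POC, the 20% row falls to 24%.

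**3. The chi-square that the plan names.** If the two methods are treated as independent samples of 30, the uncorrected chi-square has no fixed threshold of six. It needs 4 extra CGM detections if POC finds 0 patients, 7 if POC finds 3, and 8 if POC finds 6, 9 or 12. For example, 3 versus 10 gives 60 × (3×20 − 27×10)² / (30×30×13×47) = 4.81, above 3.84. With 3 versus 9 it is 60 × (3×21 − 27×9)² / (30×30×12×48) = 3.75, which is below.

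**4. What an estimate would show.** Exact (Clopper-Pearson) 95% intervals at n = 30:

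| Patients found by CGM only | Estimate | 95% CI |
|---|---|---|
| 3/30 | 10% | 2.1% to 26.5% |
| 6/30 | 20% | 7.7% to 38.6% |
| 9/30 | 30% | 14.7% to 49.4% |

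These are wide, but each tells a later trial which gains remain plausible. When no patient is found by POC only, the CGM-only proportion equals the within-patient difference.

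**The case against.** The strongest reply is that the P<.05 sentence is boilerplate. It defines a term; no go/no-go decision, success criterion or efficacy claim hangs on it, and the plan is candid about being a pilot without power. That stands. A reader might infer that P<.05 is the study's decision rule, but the documents do not say so.

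A reader might also infer that any null result would be uninformative. That goes too far: under the illustrative paired test, 30% one-way discordance would give P<.05 92% of the time. The documents also do not say what gain would be useful, so the lower rows of that table are possibilities rather than expectations.

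Nor does the text establish three tested outcomes. The list is of variables to be collected, one of them diabetes type, and the test sentences cite only blood sugar measurements and hypoglycemic events. The 14.3% is therefore an upper figure.

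Finally, the protocol states one hypothesis, about identification. A difference in mean glucose or in treatment counts would not directly support it, so it is too much to say that any significant test could pass as confirmation.

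What remains is not touched by these points. No outcome is named as primary, the title and hypothesis differ, no interval is planned, and nothing labels the tests as exploratory.

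**Conclusion.** The concern holds in a limited form. For a feasibility-sized pilot, the plan offers only P<.05 on unranked variables. A non-significant result could not be told apart from a useful gain in detection, and with two or three tests the chance of at least one false positive is roughly 10% to 14% under independence, less with correlation.

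The 7%, 57% and 92% rest on assumed one-way discordance and on an exact paired test that the plan does not name. They show how far the meaning of a null result depends on unknown rates; they do not describe the power of the plan as written. The absence of a power analysis is not itself a fault here. The plan should be changed because the change is cheap and makes the pilot's result usable, not because the study is invalid without it.

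**What to change.** Replace the P<.05 sentence with one primary estimate that matches the stated hypothesis: the within-patient difference in the proportion of patients with hypoglycemia (<70 mg/dl, the plan's own figure for a low value) identified by CGM versus by routine scheduled POC testing during the postpartum stay, with a 95% confidence interval suited to paired proportions. The definition should say whether a CGM low counts alone or only when the finger stick confirms it.

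Then:
- Say that identification, rather than a decrease in episodes, is the main question, so that title and hypothesis no longer compete.
- Label all other outcomes exploratory and report them with estimates and intervals.
- State the expected precision at n = 30, for example 6/30 = 20%, exact 95% CI 8% to 39%.
- Add to the variable list the CGM-detected lows and a flag separating routine from alarm-triggered finger sticks. Neither is listed now, and the primary estimate cannot be computed without them.
- State as a limitation that treatment prompted by an alarm can remove a low that routine POC testing would later have found, so the contrast may favor CGM.

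The cost is a few sentences, a small amount of extra data entry and no additional patients. The sponsor gives up a headline significance claim on the secondary outcomes.
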